10.13.3 Safety Reporting to the IRB

A reportable event is an adverse event or incident that has the potential to be classified by the IRB as an unanticipated problem posing risks to participants or others. An incident is determined to be reportable to the IRB when it is both:

- **probably** or **definitely** related to participation in the research
- unexpected in terms of nature, severity, or frequency

Events that meet these criteria, must be submitted to the IRB within 10 business days of discovery. **HOWEVER, if the event involved a death, investigators should report within 3 calendar days.**

If the event does not meet the reporting criteria above, the Investigator will follow the table below to determine whether the event is reportable to the IRB, and if so, when it should be reported.

Relatedness	Expectedness	Reportable to IRB?	When to Report
Unrelated or Unlikely related	Expected and Unexpected	NO	N/A
Possibly, Probably, or Definitely related	Expected	NO	N/A
Possibly related	Unexpected	YES ONLY IF: The event suggests that the research places subjects or others at greater risk than was previously known or recognized	EXPEDITED REPORTING WITHIN 10 business days; summarize at continuing review
Probably or Definitely related	Unexpected	YES	EXPEDITED REPORTING WITHIN 10 business days; Summarize at continuing review
Probably or Definitely related death	Unexpected	YES	EXPEDITED REPORTING WITHIN 3 calendar days. Summarize at continuing review

11 STATISTICAL CONSIDERATIONS

11.1 General Considerations

Descriptive statistics will be presented from the data collected in this phase 1, open-label study to address the main objectives of assessing safety, tolerability and pharmacokinetics of mAb AZD5396 and mAb AZD8076 expression at a maximum tolerated dose of dMAb AZD5396 and dMAb AZD8076. We anticipate the enrollment of up to 50 participants in the 8 cohorts.

11.2 Analytical Populations

Analysis populations include:

- The safety analysis set includes all participants who receive at least one Investigational Product administration and for whom post-dose safety data are available. Participants will be analyzed as to the dose level and cohort they were enrolled in.
- The per-protocol (PP) analysis set comprises all participants who receive all planned Investigational product administration over all planned dosing visits, have no important protocol deviations, and have valid pharmacokinetic endpoint data available until Week 48. These will be documented and tabulated prior to database lock. Participants in this sample will be analyzed as to the administration regimen to which they were enrolled.
- The modified intention-to-treat (mITT) analysis set includes all participants who receive at least one Investigational product administration and have valid pharmacokinetic endpoint data available until Week 48. Participants in this sample will be analyzed as to the dose level to which they were assigned. Analyses on the mITT sample will be considered supportive of the corresponding PP analyses.

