7.5 Day 10 (cohorts B-G only)

The following evaluations will be performed at this visit:

- Conduct targeted injection site reaction systemic and local assessment.
- Collect all present and/or new or ongoing adverse events.
- Document any present conditions and concomitant illnesses (including history of new COVID 19 diagnosis).
- Record current concomitant medications/treatments.
- Targeted physical examination.
- Record vital signs including heart rate (HR), respiratory rate (RR), blood pressure (BP), oral temperature.
- Collect blood for PT(INR) and aPTT, CBC with differential, serum chemistry, CPK.
- Collect urine for urinalysis.

- Collect serum for mAb AZD5396 and mAb AZD8076 level assessment and ADA evaluation.
- Perform 12 lead ECG.

7.6 Week 2, Week 3, Week 4, Week 5, Week 6, Week 8, Week 12, Week 16, Week 24, and Week 52

The following evaluations will be performed at these visits:

- Conduct targeted injection site reaction systemic and local assessment (cohort G, Week 5 and 6).
- Collect all present and/or new or ongoing adverse events.
- Document any present conditions and concomitant illnesses (including history of new COVID 19 diagnosis).
- Record current concomitant medications/treatments.
- Targeted physical examination.
- Record vital signs including heart rate (HR), respiratory rate (RR), blood pressure (BP), oral temperature.
- Collect blood for PT(INR) and aPTT, CBC with differential, serum chemistry, CPK
- Collect urine for urinalysis.
- Collect serum for mAb AZD5396 and mAb AZD8076 level assessment and ADA evaluation.
- Perform 12-lead ECG

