7.7 Week 32, Week 42, and additional PK/ADA measurements

The following evaluations will be performed at weeks 32 and 42:

- Collect all present and/or new or ongoing adverse events.
- Collect serum for mAb AZD5396 and mAb AZD8076 level assessment and ADA evaluation.

Participants may be asked to come in for additional PK/ADA monitoring between weeks 52 and 72, at the investigators' discretion.

Participants may be asked to come in for additional PK/ADA monitoring between weeks 72 and 98, at the investigators' discretion.

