11.3 Description of Statistical Methods

11.3.1 Safety Analyses Adverse Events

All solicited and unsolicited AEs/SAEs will be summarized by frequency per cohort and for all cohorts combined. These frequencies will be presented separately by dose and overall, by system organ class and by preferred term, the number and percentage of participants affected. Percentages, along with associated exact 90% Clopper-Pearson confidence intervals, will be based on the number of participants who are members of the safety analysis. Additional frequencies will be presented with respect to maximum severity and to strongest relationship to Investigational product administration. Multiple occurrences of the same AE will be counted only once following a worst-case approach with respect to severity and relationship to Investigational product. All SAEs and administration site events will also be summarized as above.

The main summary of safety data (treatment emergent) will be based on events occurring within 48 weeks of administration of at least one of the investigational products (as specified in Section 10.12). Safety data will also be summarized based on events occurring any time after administration of Investigational product on Day 0 to week 72.

Laboratory Data and Vital Signs

Continuous response variables per time point and changes from baseline will be summarized with descriptive statistics: mean standard deviation, minimum, median, and maximum values by time point and cohort. Categorical response variables will be summarized per time point and cohort with frequencies and percentages.

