11.3.2 Pharmacokinetic Analyses

The number and percentage of participants in which detection of monoclonal antibody mAb AZD5396 and mAb AZD8076 in serum is achieved will be summarized with a point estimate and corresponding

exact 90% Clopper-Pearson confidence interval. These will be summarized per time point within each cohort. We will also estimate the time to 50% decline from peak concentration.

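### Both pharmacokinetic analysis sets require valid PK data until Week 48, a time no PK visit window covers, so the supportive mITT set also excludes early data from participants who leave before then

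*Protocol*

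**What the plan says.** Section 11.2 of the protocol defines three analysis sets. The safety set needs one administration and post-dose safety data. The other two are the only sets defined in terms of PK data:

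- PP: all planned administrations given; in addition, participants must "have no important protocol deviations, and have valid pharmacokinetic endpoint data available until Week 48".
- mITT: participants who "receive at least one Investigational product administration and have valid pharmacokinetic endpoint data available until Week 48".

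On how the two relate: "Analyses on the mITT sample will be considered supportive of the corresponding PP analyses".

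The primary PK endpoint (Section 3.3) is detection of the two antibodies in serum. Section 11.3.2 gives the number and percentage with detection and an exact 90% Clopper-Pearson interval: "These will be summarized per time point within each cohort". It also plans an estimate of the time to 50% decline from peak, and it names no analysis set. Section 9.9.1 evaluates each participant's concentration profile from all available time points and plans Cmax, Cmin and AUC. Section 11.3.6 plans no missing-data method and reports observed values.

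After the first ten days, PK serum is drawn at the visits headed "Week 2, Week 3, Week 4, Week 5, Week 6, Week 8, Week 12, Week 16, Week 24, and Week 52", at the two late visits in "7.7 Week 32, Week 42, and additional PK/ADA measurements", and at Week 72. Cohort G is also sampled on Days 28 and 31. The optional extra draws in Section 7.7 fall between Weeks 52 and 72 and between Weeks 72 and 98.

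**The concern.** There are two problems, and the second is the more serious.

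First, the cut falls where nothing is scheduled. Someone building the analysis sets must decide whether a participant whose last sample was at Week 42 has data until Week 48, or whether a Week 52 sample is needed. The trial is open label (Section 11.5), so that decision would be made by people who can see the data.

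Second, the condition does not fit the endpoint. Whether antibody was detected at Day 7 or Week 4 does not depend on being sampled some ten months later. Under the ordinary reading, a fully dosed participant who leaves after Week 24 drops out of both sets, and all that participant's valid early samples go too. A supportive mITT analysis is useful because it is broader than PP and can show whether PP's exclusions matter. Here both sets pass through the same follow-up filter, so if departure were related to tolerability or expression, the two analyses would share the distortion and agree with each other.

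Cohorts hold 3 to 6 participants, so one exclusion removes between 1/6 (17%) and 1/3 (33%) of a cohort's primary PK data.

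**Working it through.** **1. Does any scheduled PK window contain Week 48?** Week 48 is Day 48 × 7 = 336. Late visits and windows from Tables 3 and 4:

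| Visit | Window | Days | Weeks |
|---|---|---|---|
| Week 24 | ±7 d | 161-175 | 23-25 |
| Week 32 | +8 w | 224-280 | 32-40 |
| Week 42 | ±2 w | 280-308 | 40-44 |
| Week 52 | ±7 d | 357-371 | 51-53 |
| Week 72 | ±7 d | 497-511 | 71-73 |

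Day 336 lies in none of them. The gap runs from Day 308 to Day 357, and the optional draws in Section 7.7 begin only at Week 52.

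**2. Who is in which set?** Take a participant who receives every planned dose, gives valid samples through Week 24 and then withdraws.

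- Section 11.2, PP: no PK data until Week 48, so excluded.
- Section 11.2, mITT: same condition, so excluded.
- Section 11.3.2: detection at each visit through Week 24 is observed and could be summarised.
- Section 9.9.1: all available time points are to be used.
- Section 11.3.6: observed values are to be reported.

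The last three would use the data. The set definitions remove them.

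**3. How likely is at least one such loss?** The protocol states no dropout rate, so d is assumed at 5%, 10% and 20%, with independent departures. P(at least one of n leaves) = 1 − (1 − d)^n.

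| n | d = 5% | d = 10% | d = 20% |
|---|---|---|---|
| 6 | 1 − 0.95^6 = 0.265 | 1 − 0.90^6 = 0.469 | 1 − 0.80^6 = 0.738 |
| 5 | 0.226 | 0.410 | 0.672 |
| 3 | 0.143 | 0.271 | 0.488 |

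These are probabilities before any replacement under Section 8.2.

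**4. What does a loss do to precision?** Section 11.4 states that 90% intervals for samples of 6 will be no wider than 0.694. The exact 90% Clopper-Pearson interval for 3 of 6 is 0.153 to 0.847, width 0.694, which reproduces that figure. The maximum width over attainable counts is then:

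| n | Maximum 90% width |
|---|---|
| 6 | 0.694 |
| 5 | 0.734 |
| 4 | 0.805 |
| 3 | 0.848 |
| 2 | 0.949 |

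(Table 6 shows 0.744 for N=5 because it evaluates the interval at 2.5 events; 0.734 is the largest width at a whole number of events.) One exclusion from a cohort of 6 costs 0.734 − 0.694 = 0.040 of width. One exclusion from a cohort of 3 costs 0.949 − 0.848 = 0.101.

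**The case against.** The strongest reply is that "until" names a period, not a sample. A reader might infer from the missing visit that nobody can qualify for either set. The documents do not support that. A participant sampled at every visit through Week 42, or through Week 52, can fairly be said to have data until Week 48. Section 9.9.1 also allows unscheduled PK samples when antibody is detected at Week 6. What stands is that the text does not say which late sample suffices.

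It can also be argued that the phrase means any valid data in the period up to Week 48, which would exclude almost nobody. Sections 9.9.1, 11.3.2 and 11.3.6 lean that way. Section 11.2 does not say so, however, and as an eligibility condition its ordinary meaning is follow-up to that time.

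A follow-up condition in PP is defensible in itself: AUC and time to 50% decline need late samples. That is accepted. The difficulty is repeating the condition in mITT and applying it to detection at early visits.

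Replacement is a partial answer. Table 2, note d, defines n as evaluable participants and allows up to 50 to be dosed. Replacement may restore a cohort's size, but it is discretionary and does not bring back the excluded participant's data.

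Finally, a reader might extend the point to safety, where Section 11.3.1 says "The main summary of safety data (treatment emergent) will be based on events occurring within 48 weeks of administration". That extension fails. It is an interval for counting events, adverse events are collected throughout participation, no visit is needed, and a second summary runs to Week 72. Only the pointer to Section 10.12 is wrong, since that section covers device complaints.

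**Conclusion.** The point holds for the two PK sets. The Week 48 condition matches no scheduled PK window, and on its ordinary reading it removes valid primary-endpoint data on anyone who leaves earlier. Because mITT shares the condition with PP, it cannot serve as a check on PP for selection by dropout.

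The size depends on a dropout rate the protocol does not give. Across assumed rates of 5% to 20%, the chance that a cohort of 6 loses at least one participant from both sets is 26% to 74%; for a cohort of 3 it is 14% to 49%. The loss of precision is modest for one participant in 6 and larger in a cohort of 3. Bias from departures related to tolerability is possible, but nothing in the protocol shows that it will occur.

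The trial is descriptive, with no hypothesis test, and other sections point towards using all the data. This is something that should be fixed; it does not invalidate the PK analysis.

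**What to change.** In Section 11.2:

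- Define the mITT (PK) set as all participants with at least one administration and at least one valid post-dose concentration. State that the denominator at each time point is the number sampled at that time point.
- If PP keeps a follow-up condition, tie it to a scheduled PK visit (Week 42 or Week 52, for example) and apply it only to the parameters that need long follow-up, namely AUC and time to 50% decline. Do not apply it to per-time-point detection.

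Editorial: correct the Section 10.12 cross-reference in Section 11.3.1. The 48-week safety interval needs no change.

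The cost is wording only, with no new visits, samples or participants. The one drawback is that denominators may differ between time points, so each table should print them.

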11.3 Description of Statistical Methods

11.3.1 Safety Analyses Adverse Events

All solicited and unsolicited AEs/SAEs will be summarized by frequency per cohort and for all cohorts combined. These frequencies will be presented separately by dose and overall, by system organ class and by preferred term, the number and percentage of participants affected. Percentages, along with associated exact 90% Clopper-Pearson confidence intervals, will be based on the number of participants who are members of the safety analysis. Additional frequencies will be presented with respect to maximum severity and to strongest relationship to Investigational product administration. Multiple occurrences of the same AE will be counted only once following a worst-case approach with respect to severity and relationship to Investigational product. All SAEs and administration site events will also be summarized as above.

The main summary of safety data (treatment emergent) will be based on events occurring within 48 weeks of administration of at least one of the investigational products (as specified in Section 10.12). Safety data will also be summarized based on events occurring any time after administration of Investigational product on Day 0 to week 72.

Laboratory Data and Vital Signs

Continuous response variables per time point and changes from baseline will be summarized with descriptive statistics: mean standard deviation, minimum, median, and maximum values by time point and cohort. Categorical response variables will be summarized per time point and cohort with frequencies and percentages.

11.3.2 Pharmacokinetic Analyses

The number and percentage of participants in which detection of monoclonal antibody mAb AZD5396 and mAb AZD8076 in serum is achieved will be summarized with a point estimate and corresponding

exact 90% Clopper-Pearson confidence interval. These will be summarized per time point within each cohort. We will also estimate the time to 50% decline from peak concentration.

11.3.3 Disposition

Disposition will be summarized by cohort and overall and will include the number and percentage enrolled, the number and percentage who received each planned dose and the number who completed the trial. The number and percentage of participants who discontinued will be summarized overall and by reason. The number in each analysis population will also be presented.

11.3.4 Demographic and Other Baseline Characteristics

Demographic and baseline data, vital signs, medical history, concomitant illnesses, and current medications/treatments will be summarized with descriptive statistics: mean, standard deviation, minimum, median and maximum values for continuous variables, and percentages for categorical variables, by cohort.

11.3.5 Interim Analyses

Interim analyses will be conducted in response to safety events as they emerge. For reasons of futility or safety issues, the DSMB could recommend stopping enrollment at any time.

11.3.6 Missing Values

The study is small, and we will be replacing subjects who do not receive medication per Investigator discretion. Subjects in cohorts B, C, D, E, and F may be replaced if they do not receive both the Day 0 and the Day 3 doses. Subjects in cohort G may be replaced if they do not receive all four of the Day 0, 3, 28, and 31 doses. Subjects in these cohorts who only receive Day 0 doses and want to continue in the study will be included in the A1 or A2 group for analysis. We do not anticipate employing methods for missing data and will report summaries from reported values.

11.4 Sample Size/Power

Our analyses will focus on estimation, and not on hypothesis testing. No formal power analysis is applicable to this study. We will, however, describe the precision available for descriptive statistics used to summarize the data. For proportions, our samples will be either N=3, N=5, N=6, or N=24, with target estimates of 30% DLTs. CI width varies with event frequency, as shown in Table 6. Our 90% CIs will be no wider than 0.694 for the samples of 6, or 0.361 for the overall sample of 24. For continuous measures, samples of 6 and 24 will yield standardized CIs of 1.64 SDs and 0.70 SDs respectively.

Table 6. Width of 95% CIs

Sample	Pr=0.05	Pr=0.1	Pr=0.2	Pr=0.3	Pr=0.4	Pr=0.5
N=3	0.676	0.716	0.785	0.835	0.865	0.875
N=5	0.510	0.562	0.647	0.703	0.734	0.744
N=6	0.456	0.512	0.598	0.653	0.684	0.694
N=24	0.191	0.239	0.300	0.335	0.355	0.361

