4 STUDY PLAN

4.1 Study Design

This will be a Phase 1, open label, single center, dose escalation study to evaluate the safety, tolerability, and pharmacokinetic profile of mAb AZD5396 and mAb AZD8076 following delivery of optimized dMAb AZD5396 and dMAb AZD8076 with different doses of Hylenex® Recombinant, administered by intramuscular injection (IM) followed immediately by electroporation (EP) using the CELLECTRA™ 2000 with side port needle device, in a five-dose (8 cohort) regimen in healthy adults.

Up to 50 healthy volunteers 18 to 60 years of age will be enrolled in this study and evaluated across eight cohorts (n=3 to 6 per cohorts A1, A2, B, C, and D; n=5 per cohorts E, F, and G). Participants will be administered dMAb AZD5396 and dMAb AZD8076 at a five-dose level of each plasmid:

- 0.5 mg single-dose (cohort A1),
- 1 mg single-dose (cohort A2),
- 1 mg two-dose (cohorts B and F),
- 2 mg two-dose (cohort C),
- 0.25 mg two-dose (cohort D),
- 4 mg two-dose (cohort E), and
- 2 mg four-dose (cohort G).

Participants will receive two injections (one per dMAb) into the arm (deltoid)/leg (quadriceps) region at Day 0 alone (groups A1 and A2) or on day 0 and 3 (groups B-F) or on days 0, 3, 28, 31 (cohort G). Injections may be given in different arms or in an arm (deltoid) and a leg (quadriceps). If preferred or needed both doses can be done in the deltoid region or the lateral quadriceps, although the injections should be in different areas separated by at least 2 cm. The Day 3 injections may repeat an area already used on Day 0 as long as separated by at least 2 cm. The Day 31 injections may repeat an area already used on Day 28 as long as separated by at least 2 cm. The Day 28 injections may repeat an area already used on Day 0 or Day 3 injections with no separation required given the time span between injections.

This study will adhere to a dose escalation scheme as described in [Figure 2](#).

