Participants will be enrolled sequentially beginning with Cohort A1. The first participant in cohort A1 will be dosed 0.5 mg of each product once on Day 0 following confirmation of eligibility criteria. If no stopping event (DLT) is observed (see Section [10.10](#)) after 14 days of the initial dose, the remaining two participants in that cohort A1 will be dosed three days apart. If there are 0 DLT events after 14 days of the initial dosing of the third subject, cohort A2 will open and will follow the same schedule. Same process will be followed for the next cohorts with a total of 6 participants enrolled in each of cohort B to C (See [Figure 2](#)), 1 sentinel participant will be enrolled initially and, after 14 days of observation, the additional 5 participants will be enrolled three days apart each. If there are 0 DLT events past 14 days after the initial dosing of the last participant, the next cohort will open. Because cohorts D F, & G are a similar or lower dose and the safety profile have been already established in previous cohorts, the 14-day waiting periods will not apply to Cohorts D, F, or G. Even though the levels of expression observed in cohorts A-D are way below the levels seen when the monoclonal antibodies are given as protein, Cohort E will receive a higher dose which will require a 14 day waiting period after the dosing of the first participant at this level. Every participant in Cohort E following the 14 day waiting period will be dosed 3 days apart as done in other cohorts. Any DLT will be reported to the FDA in an expedited manner.

Table 2. Dosing Arms and Regimens

Cohort	Study Product	Dose Schedule	n	No. injections per dose (dose formulation in mg) 2 injections are given on each day	Hylenex dose per injection	Final volume per injection	EP parameters	Total dose of each dMAb (mg)
A1	dMAb AZD5396 and dMAb AZD8076	Day 0	3	1x (0.5 mg dMAb AZD5396) + 1x (0.5 mg dMAb AZD8076)	68U	0.5 mL	OpBlock 0078	0.5 mg dMAb AZD5396 + 0.5 mg dMAb AZD8076
A2	dMAb AZD5396 and dMAb AZD8076	Day 0	3	1x (1mg dMAb AZD5396) + 1x (1 mg dMAb AZD8076)	135U	1 mL	OpBlock 0078	1 mg dMAb AZD5396 + 1 mg dMAb AZD8076
B	dMAb AZD5396 and dMAb AZD8076	Day 0, 3	6 (3+3)	2x (0.5 mg dMAb AZD5396) + 2x (0.5 mg dMAb AZD8076)	66.5U	0.5 mL	OpBlock 0078	1 mg dMAb AZD5396 + 1 mg dMAb AZD8076
C	dMAb AZD5396 and dMAb AZD8076	Day 0, 3	6 (3+3)	2x (1 mg dMAb AZD5396) + 2x (1 mg dMAb AZD8076)	135U	1 mL	OpBlock 0078	2 mg dMAb AZD5396 + 2 mg dMAb AZD8076

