D	dMAb AZD5396 and dMAb AZD8076	Day 0, 3	6 (3+3)	2x (0.25 mg dMAb AZD5396) + 2x (0.25 mg dMAb AZD8076)	34U	0.25 mL	OpBlock 0078	0.5 mg dMAb AZD5396 + 0.5 mg dMAb AZD8076
E	dMAb AZD5396 and dMAb AZD8076	Day 0, 3	5	2x (2 mg dMAb AZD5396) + 2x (2 mg dMAb AZD8076)	75U (0.5 mL)	0.70 mL	OpBlock 0078	4 mg dMAb AZD5396 + 4 mg dMAb AZD8076
F	dMAb AZD5396 and dMAb AZD8076	Day 0, 3	5	2x (0.5 mg dMAb AZD5396) + 2x (0.5 mg dMAb AZD8076)	75U (0.5 mL)	0.55 mL	OpBlock 0070	1 mg dMAb AZD5396 + 1 mg dMAb AZD8076
G	dMAb AZD5396 and dMAb AZD8076	Day 0, 3, 28, 31	5	4x (0.5 mg dMAb AZD5396) + 4x (0.5 mg dMAb AZD8076)	75U (0.5 mL)	0.55 mL	OpBlock 0078	2 mg dMAb AZD5396 + 2 mg dMAb AZD8076
	TOTAL		44-50^d					

^a All subjects will receive the study product by IM route of administration. All doses of optimized dMAb AZD5396 and dMAb AZD8076 will be prepared with Hylenex® less than 4 hours before dosing of subjects. Doses of Hylenex will vary depending on the cohort to allow for a different volume per injection

^b Use of CELLECTRA™ 2000 with Side Port needle, OpBlock 0078 and 5P-IM Side Port Array or Profusion Therapeutic Infusion needle (G47574) for Cohorts A-E & G.

^c Use of CELLECTRA™ 2000 with Side Port needle, OpBlock 0070 and 5P-IM Side Port Array for Cohort F.

^d Note that the n is defined as evaluable participants. Due to partial doses or early dropouts, we may dose up to 50 participants total to reach enough evaluable participants in each cohort. See Protocol section [8.2](#) which describes replacing participants.

The decision to open new cohorts in the clinical trial is justified by several key factors. Firstly, ensuring safety is of utmost importance in any clinical trial. By introducing additional cohorts, we will gather more data on the safety profile of the investigational product.

Secondly, evaluating the levels of expression of dMAbs is crucial for assessing the efficacy of this approach. The expression levels directly impact the therapeutic potency and effectiveness *in vivo*. By expanding the cohorts, we will gather a larger sample size and thereby obtain more reliable data on the expression levels of dMAbs in different individuals. This broader understanding of expression levels will aid in determining optimal dosages and predicting the treatment's potential success.

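### Section 11.4 gives precision for an overall sample of 24, which is Cohorts A1 to D only; Table 2's cohort sizes add to 39 evaluable, and its printed total of 44-50 has an unexplained lower end

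*Protocol*

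**What the plan says.** Protocol Section 4.1 gives cohort sizes in its text as "n=3 to 6 per cohorts A1, A2, B, C, and D; n=5 per cohorts E, F, and G". Table 2 in the same section lists 3, 3, 6, 6, 6, 5, 5 and 5 for Cohorts A1, A2, B, C, D, E, F and G, and prints a total of 44-50. Footnote d to that total says "Note that the n is defined as evaluable participants", and adds that as many as 50 may be dosed because some participants may receive partial doses or drop out early.

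Section 11.1 says "We anticipate the enrollment of up to 50 participants in the 8 cohorts". Section 11.3.1 plans adverse event summaries by cohort and over all cohorts together, with exact 90% Clopper-Pearson intervals on the safety analysis set.

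Section 11.4 gives precision for N=3, 5, 6 and 24: "Our 90% CIs will be no wider than 0.694 for the samples of 6, or 0.361 for the overall sample of 24". For continuous measures it gives 1.64 SD at N=6 and 0.70 SD at N=24. Table 6, which holds the widths, is titled as showing 95% intervals.

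**The concern.** The protocol carries several incompatible sample sizes: 24 in Section 11.4, 39 by adding Table 2, 44 as the lower end of the printed total, and 30 to 45 from the text of Section 4.1. The 50 is consistent throughout as an upper limit. A reader on the DSMB, at the IRB or at the agency cannot tell which number is the planned evaluable sample, or which sample the overall precision describes.

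Section 11.4 is also inconsistent within itself. It includes N=5, and only Cohorts E, F and G have five participants, yet its overall sample leaves those cohorts out. At stake is whether the stated overall precision belongs to the trial as now designed.

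**Working it through.** **Inputs.** Cohort sizes and total: Table 2 and footnote d. Cohort ranges: text of Section 4.1. Interval method and level: Section 11.3.1 (exact Clopper-Pearson, 90%). Stated widths: Section 11.4 and Table 6.

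**Step 1: totals.**
- Table 2: 3 + 3 + 6 + 6 + 6 + 5 + 5 + 5 = 39.
- Cohorts A1 to D: 3 + 3 + 6 + 6 + 6 = 24, exactly the overall sample in Section 11.4.
- Cohorts E to G: 5 + 5 + 5 = 15, and 24 + 15 = 39.
- Section 4.1 text: minimum 5×3 + 3×5 = 30; maximum 5×6 + 3×5 = 45. The maximum is Table 2 with A1 and A2 each at 6 (39 + 3 + 3 = 45).

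So 44 is neither the Table 2 sum nor an end of the Section 4.1 range, and 24 is below the smallest total that Section 4.1 allows.

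**Step 2: reproduce the plan's widths.** With x = N×p (non-integer x allowed) and α = 0.10, the width is

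Beta quantile(1−α/2; x+1, N−x) − Beta quantile(α/2; x, N−x+1).

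All 24 entries of Table 6 reproduce to three decimals. At p=0.5:

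| N | Printed | 90% width | 95% width |
|---|---|---|---|
| 6 | 0.694 | 0.694 | 0.764 |
| 24 | 0.361 | 0.361 | 0.418 |

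The table therefore holds 90% widths, as the text of Section 11.4 says. Its title is wrong.

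For a mean, the standardised width is 2×t(0.95; N−1)/√N:
- N=6: 2×2.015/2.449 = 1.645 SD (printed 1.64).
- N=24: 2×1.714/4.899 = 0.700 SD (printed 0.70).

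The method is confirmed, so only the overall N is in question.

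**Step 3: the same formulas at the eight-cohort totals (90%).**

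| N | p=0.05 | 0.1 | 0.2 | 0.3 | 0.4 | 0.5 | Mean, SD units |
|---|---|---|---|---|---|---|---|
| 24 (stated) | 0.191 | 0.239 | 0.300 | 0.335 | 0.355 | 0.361 | 0.70 |
| 39 (Table 2 sum) | 0.142 | 0.182 | 0.232 | 0.261 | 0.276 | 0.281 | 0.54 |
| 45 (Section 4.1 maximum) | 0.131 | 0.168 | 0.215 | 0.242 | 0.257 | 0.261 | 0.50 |
| 50 (dosing cap) | 0.123 | 0.159 | 0.203 | 0.229 | 0.243 | 0.248 | 0.47 |

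The last row matters because Section 11.2 puts in the safety set everyone with at least one administration and post-dose safety data. Participants who were dosed and then replaced stay in it, so the pooled safety denominator can exceed 39.

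**The case against.** The strongest defence is that nothing in Section 11.4 misleads in a harmful direction. The width of 0.361 is computed correctly for N=24 and is stated as an upper bound. That bound still holds at 39 and at 50. The cohort-level widths match the current cohort sizes, the pooled row drives no escalation or stopping decision, and no hypothesis is tested. All of this stands, and it limits the point to a correction of text.

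Four stronger readings are tempting, but the documents do not support them.

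- A reader might infer that the sponsor claims 44 evaluable participants, an overstatement of 5. Because footnote d speaks both of evaluable n and of a dosing cap, 44-50 could be meant as a range of participants dosed. The cell is unexplained; it does not prove such a claim.
- A reader might infer that the room for replacements is misstated. The protocol gives no figure for it, and the room depends on whether A1 and A2 stay at 3 or grow to 6.
- A reader might infer that the trial is left without a valid sample size rationale. The modified 3+3 scheme in Section 4.2 and the widths for N=3, 5 and 6 also support the size, and both are untouched.
- A reader might call 24 a leftover from a five-cohort design. The match with A1 to D and the presence of N=5 make this plausible, but the protocol does not say where 24 comes from.

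The defence does not rescue the label. Under no reading of the current protocol is 24 the overall sample.

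**Conclusion.** The point holds as an inconsistency in stated figures. Table 2's evaluable numbers add to 39 against a printed 44-50, with the 44 unexplained. Section 11.4's overall sample of 24 covers five of the eight cohorts. The overall precision it states (0.361 and 0.70 SD) is not that of the eight-cohort trial: at the planned 39 it is 0.281 and 0.54 SD, and at the cap of 50 it is 0.248 and 0.47 SD. The error understates precision. Per-cohort precision, enrolment and dose escalation are unaffected.

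This rests on reading the Table 2 entries as planned evaluable numbers, as footnote d says, and on the 90% Clopper-Pearson method of Section 11.3.1, which reproduces every entry of Table 6.

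**What to change.** - **Table 2:** give the total as 39 evaluable, with up to 50 dosed including replacements, and remove or explain the 44.
- **Section 4.1:** reconcile the range of 3 to 6 per cohort for A1 to D (total 30 to 45) with the fixed entries in Table 2.
- **Section 11.4 and Table 6:** replace N=24 by N=39, with 90% widths 0.142, 0.182, 0.232, 0.261, 0.276 and 0.281, and 0.54 SD for continuous measures. Add that the safety set may reach 50, where the maximum width is 0.248 and the standardised width 0.47 SD.
- **Table 6 title, and its entry in the list of tables:** change 95% to 90%, so that the new row is not mislabelled.

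The cost is a few sentences, one table row and one title. Enrolment, conduct and the planned analyses do not change.
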